## **2. Objectives**

Primary Objective:

- To evaluate the effect of foot reflexology on anxiety symptoms, measured by the Beck Anxiety Inventory (BAI).

Secondary Objectives:

- To assess changes in psychological well-being and relaxation using the Tension-Anxiety subscale of the Profile of Mood States (POMS, reduced version).
- To record and analyze adverse effects related to the interventions.

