## **3. Study Design**

This is a randomized, parallel, controlled, double-blind clinical trial with two arms:

1. Foot reflexology intervention.
2. Sham reflexology (control group).

The study will last approximately 5 weeks, with 10 intervention sessions per participant.

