## **6. Outcome Measures**

Primary Outcome:

- Reduction in anxiety symptoms assessed by Beck Anxiety Inventory (BAI).
- Score range: 0 to 63.
- Higher scores indicate worse anxiety.

- Time points: baseline, after session 5, after session 10.

Secondary Outcomes:

- Tension-Anxiety Subscale of the Profile of Mood States (POMS – reduced version).
- Score range: 0 to 36.
- Higher scores indicate worse tension-anxiety.
- Time points: after each of the 10 sessions.
- Adverse effects.
- Recorded during and after each session.
- Frequency and intensity analyzed descriptively.

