## **9. Statistical Analysis Plan**

Descriptive statistics (mean  $\pm$  SD) will be used for quantitative variables.

- Primary outcome (BAI): Repeated measures ANOVA (Group  $\times$  Time) with post-hoc Bonferroni.

- Secondary outcomes (POMS): Repeated measures ANOVA (Group × Time).
  - Adverse effects: Frequency distribution and Chi-square tests.
- Significance level:  $p < 0.05$ . SPSS (IBM, v.29) will be used.

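### Does listing adverse effects as descriptive in section 6 but with chi-square tests in section 9 call for a change to the plan?

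*Protocol*

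**What the plan says.** Section 2 makes adverse effects a secondary objective: "To record and analyze adverse effects related to the interventions". It does not say whether that means a test.

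Section 6 lists them among the secondary outcomes, "Recorded during and after each session", and gives the analysis as "Frequency and intensity analyzed descriptively".

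Section 9 gives the analysis of the same outcome as "Adverse effects: Frequency distribution and Chi-square tests", under a general significance level of 0.05. It does not mention intensity and does not say what the chi-square table counts: participants, sessions or events.

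Section 3 describes a two-arm trial of about 5 weeks, "with 10 intervention sessions per participant".

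**The concern.** Two things catch the eye.

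First, one section describes and the other tests. Read strictly, an analyst could decide after seeing the event counts whether to report a p-value.

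Second, the test has no stated unit, and the design produces up to ten records per person. A chi-square test assumes independent records. Someone whose feet are sore after one session is more likely than others to be sore after the next, so a table of sessions would overstate the information and give p-values that are too small. The stake would be a spurious difference in tolerability between reflexology and sham, on an outcome tied to a stated objective. The BAI comparison would not be affected.

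**Working it through.** The protocol states no figure on this point, so there is nothing to reproduce. Two checks apply.

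**1. The two sections side by side**

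| Element | Section 6 | Section 9 |
|---|---|---|
| Frequency | described | frequency distribution |
| Intensity | described | not mentioned |
| Comparison of arms | not mentioned | chi-square tests |
| Unit of the test | – | not stated |

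No cell of one column forbids what stands in the other. Section 6 does not say that description is the only analysis. Section 9, the designated analysis section, keeps the frequency description and adds a test. An analyst who tabulates frequency and intensity by arm and also runs the chi-square test has complied with both.

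**2. What the open unit could cost**

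From the protocol: 10 sessions per participant and a significance level of 0.05. Assumed, because the protocol gives none of them: 20, 30 or 50 participants per arm; an effect at 5% or 10% of sessions; within-participant correlation ρ of 0.05 to 0.3.

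*If sessions were pooled.* The design effect is DE = 1 + (10 − 1)ρ = 1 + 9ρ, and the actual type I error is 2·(1 − Φ(1.96/√DE)).

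| ρ | DE | 1.96/√DE | Type I error |
|---|---|---|---|
| 0.05 | 1.45 | 1.628 | 0.104 |
| 0.1 | 1.9 | 1.422 | 0.155 |
| 0.2 | 2.8 | 1.171 | 0.241 |
| 0.3 | 3.7 | 1.019 | 0.308 |

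Beta-binomial simulation agrees (0.099–0.105, 0.151–0.157, 0.236–0.245 and 0.308–0.316) and barely moves with arm size or event rate.

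*If participants with at least one effect are counted.* The share affected is 1 − B(a, b+10)/B(a, b), with a = p(1/ρ − 1) and b = (1 − p)(1/ρ − 1), where p is the per-session rate. For ρ = 0.05, 0.1, 0.2 and 0.3:

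- p = 0.05: 0.342, 0.300, 0.239, 0.197
- p = 0.10: 0.576, 0.516, 0.427, 0.359

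Expected counts per arm therefore run from 20 × 0.197 = 3.9 to 50 × 0.576 = 28.8. Enumerating all pairs of binomial outcomes at these shares gives the type I error in the first row below. The second row is for one effect type seen in 2%, 5% or 10% of participants, again with 20 to 50 per arm.

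| Table of participants | Pearson chi-square | Fisher's exact test |
|---|---|---|
| Any effect | 0.043–0.057 | 0.021–0.035 |
| Single rare effect | 0.0008–0.054 | 0.0000–0.018 |

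So at participant level the planned chi-square test is near nominal or conservative. Moving to Fisher's test for sparse tables would correct no inflation. Where such a rule would mostly apply, to rare single effects, it would take the size down to 0–1.8%.

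**The case for a change.** The best case for acting is that this is not mere silence. The protocol describes the analysis twice and not identically, both texts are current, and section 2 makes the outcome an objective. A separate SAP that only described would depart from section 9, and one that tested would go further than section 6 announces. Blinding of the data analysts (section 7) does not close the gap, since a test on coded arms still yields a p-value and event counts are visible without group labels. The repair would be a few words.

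Some of this stands. The wording is not aligned, section 9 leaves out intensity, and any test that is run should count participants or use a method that allows for repeated records. Blinding limits choosing in favour of a known arm but does not remove all discretion.

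The step from there to a required change does not stand. The strong figures, 10% to 31%, depend on a session-level table that no section plans. The unit of a safety table is the kind of detail usually left to a SAP, which may exist here but is not shown. The obvious repair would also still leave the sponsor to choose whether to keep a test.

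**Conclusion.** No change to the plan follows. The difference between sections 6 and 9 is a soft mismatch of wording: both can be carried out together, and neither rules the other out. The unit of the chi-square table is a gap that an analyst fills sensibly by counting each participant once. Done that way, the test holds its level: 4.3% to 5.7% for any effect, and 0.1% to 5.4% for rare single effects.

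These figures rest on assumed arm sizes of 20 to 50, per-session rates of 5% or 10%, correlations of 0.05 to 0.3, and single-effect rates of 2% to 10%. The conclusion does not depend on their exact values. It depends on the absence of any plan to pool sessions. If a SAP did specify a chi-square test on session records, the inflation shown above would apply and the point would have to be reopened. The outcome is secondary, section 10 expects mild local reactions and no serious effects, and the BAI analysis is unaffected.

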## **10. Risks and Benefits**

Risks: Mild local reactions in the feet, such as redness, sensitivity, discomfort, or muscle soreness, which typically resolve within 48–72 hours. Transient tingling may occur. Serious adverse effects are not expected.

Benefits: Possible reduction in anxiety symptoms, improved relaxation and well-being, and contribution to scientific knowledge about reflexology.

## **11. Ethical Considerations**

The study will be conducted in accordance with the Declaration of Helsinki and approved by the Institutional Ethics Committee. All participants will provide written informed consent before enrollment.

